11.1.	INTERNATIONAL STANDARDS	32
11.2.	DELEGATION OF INVESTIGATOR DUTIES	32
11.3.	SUBJECT INFORMATION AND INFORMED CONSENT	32
11.4.	PATIENT INSURANCE	32
11.5.	PERSONAL DATA PROTECTION/CONFIDENTIALITY	32
11.6.	LEGAL APPROVALS, ANNUAL PROGRESS REPORT AND END OF STUDY REPORT	33
11.6.1.	Submission of Documents at Study Start.....	33
11.6.2.	Annual Progress Report.....	33
11.6.3.	End of Study Report	33
12.	AMENDMENTS TO THE CLINICAL INVESTIGATION PLAN	33
13.	EARLY TERMINATION OR SUSPENSION OF THE INVESTIGATION	34
14.	RECORD RETENTION.....	34
15.	STUDY FINANCIAL ARRANGEMENTS.....	35
16.	PUBLICATION POLICY	35
17.	LIST OF ABBREVIATIONS	35
18.	REFERENCES.....	36

List of Appendices

APPENDIX 1	PATIENT INFORMATION SHEET AND INFORMED CONSENT FORM
APPENDIX 2	SAMPLE CASE REPORT FORM

STUDY SUMMARY

Title	Polyethylene Wear Study on the Triathlon Total Knee Prosthesis_A Comparison of a Highly-crosslinked and a Crosslinked PE in-vivo
Protocol Number	TriX3_2009
Phase	Post-marketing
Sponsor	Stryker SA, Montreux, Switzerland
Study design	A Prospective Randomized Single Centre RSA Study
Study Duration	12 months enrolment period + up to 5 year follow-up for each case = 6 years total duration.
Study Centre(s)	1
Objectives	
The primary objective is the assessment of the in vivo wear of the two randomized polyethylene inlay types N2Vac and X3 by means of Roentgen Stereophotogrammetry.
 
The secondary objective is the assessment of prosthetic migration results after two years of the Triathlon CS Peri-Apatite coated tibial component by means of Roentgen Stereophotogrammetry.
 
The third objective will be the prediction of the long-term survival of the Triathlon CS Peri-Apatite coated tibial components based on the two-year migration patterns combined with clinical factors and radiographic aspects.
 
Safety data will be collected

Primary endpoint	In-vivo wear of N2Vac inlay vs. X3 inlay
Indication	Primary total knee replacement
Study device / control device	Triathlon CS total knee system
Number of Subjects	100 Patients

Inclusion Criteria	
Inclusions:
 
1. Patient is able to understand the meaning of the study and is willing to sign the EC approved, study specific Informed Patient Consent Form.2. Patients with a pre-operative knee score of < 70.3. Patients scheduled to undergo primary total knee replacement with any of the following indication.
– Painful and disabled knee joint resulting from osteoarthritis.– One or more compartments are involved.4. Need to obtain pain relief and improve function.5. Ability and willingness to follow instructions, including control of weight and activity level, and to return for follow-up evaluations.6. A good nutritional state of the patient.7. Full skeletal maturity of the patient, patients who are at least 18 years of age.8. Patients of either sex.
--------------------	--


Exclusion Criteria
	
Exclusions:
 
 1. The subject is morbidly obese, defined as Body Mass Index (BMI) of > 40. 2. Skeletal immaturity of the patient, patients who are less than 18 years of age. 3. Patient has a flexion contracture of 15° and more. 4. Patient has a varus/valgus contracture of 15° and more. 5. Patients with a pre-operative knee score of >70. 6. The subject has a history of total or unicompartmental reconstruction of the affected joint. 7. The subject will be operated bilaterally. 8. Patients who had a Total Hip Arthroplasty (THA) on contralateral and/or ipsilateral side within the last year that is considered to have an unsatisfactory outcome (Patients with contralateral and/or ipsilateral THA > 1 year ago with good outcome can be included in the study). 9. Patients who had a Total Knee Arthroplasty (TKA) on contralateral side within the last 6 months that is considered to have an unsatisfactory outcome. (Patients with contralateral TKA > 6 months ago with good outcome can be included in the study). 10. The subject has an active or suspected latent infection in or about the knee joint 11. Osteomyelitis 12. Sepsis 13. Patients who will need lower limb joint replacement for another joint within one year. 14. The subject has a neuromuscular or neurosensory deficiency, which would limit the ability to assess the performance of the device. 15. The subject has a systemic or metabolic disorder leading to progressive bone deterioration. 16. The subject is immunologically suppressed or receiving steroids in excess of normal physiological requirements. 17. The subject's bone stock is compromised by disease or infection which cannot provide adequate support and/or fixation to the prosthesis. 18. The subject has had a knee fusion to the affected joint. 19. Female patients planning a pregnancy during the course of the study. 20. The patient is unable or unwilling to sign the Informed Consent specific to this study
---------------------------	---

Patient evaluations will be performed according to the schedule below:

Table 1 – Evaluation schedule

	Pre -op	Op	< 1wk (prior to discharge)	6wk	3m	6m	1yr	2yr	5 yr
Range (weeks)				±4d	±1wk	±2wks	±4wks	±4wks	±6ks
Demographic Information	✓								
Historical Record	✓								
Clinical Evaluation			✓	✓	✓	✓	✓	✓	✓
Operative Record		✓							
Knee Society Score	✓			✓	✓	✓	✓	✓	✓
SF-36	✓			✓	✓	✓	✓	✓	✓
EQ 5-D	✓			✓	✓	✓	✓	✓	✓
Lower-Extremities Activity	✓			✓	✓	✓	✓	✓	✓

1.1. Introduction

The most common causes for failure after more than 2 years after primary total knee surgery are polyethylene wear and aseptic loosening (Dennis, 2004; Fehring et al., 2001; Sharkey et al., 2002). Cumulative 10 year revision rates of total knee arthroplasty (according to the Swedish Knee register report) have generally decreased over the past 25 years probably due to improvements in implant design, more accurate instrumentation and polyethylene quality. However, there is a general trend towards treating younger patients and these younger and probably more active patients are likely to generate more wear and hence this may contribute to a new increase of wear and revision rates seen in (younger) patients.

The Posterior Stabilized (PS) knee prosthesis is the most implanted total knee prosthesis design in the world. In PS knees articulation of the femoral component is facilitated by the use of a post and cam interaction providing the anterior-posterior sliding necessary to reach optimal (high) flexion. Research indicates that the high degree of tibial-femoral conformity and stability, which characterizes PS knees, plays an important role in the long-term durability and survivorship of 90% after 15 year of this design (Aglieiti *et al.*, 1999, Stern & Insall, 1992). However, it has also been shown that posterior stabilized implants contribute to additional wear debris. Especially at anterior and posterior locations of the post severe wear has been observed (Puloski et al., 2001).

Ultra high molecular weight polyethylene (UHMWPE) is nowadays the standard material used for the articulating surface. Recently a cross-linking process improved the mechanical properties of polyethylene with double or even triple cross-linking procedures arising. An example of a triple cross-linked polyethylene is X₃ (Stryker, Warsaw, USA). Theoretically and *in vitro* X3-polyethylene has improved wear resistance over conventional and current generation cross-linked polyethylene. It improves wear reduction over conventional polyethylene with 97%; the mechanical properties are maintained so that structural fatigue, yield strength and ultimate tensile strength are equivalent to virgin polyethylene and it resists oxidation. However, so far no clinical *in vivo* data has shown the benefits of this new material for tibial bearings. Combining this new material with a PS design should theoretically lead to superior wear characteristics and consequently long-term durability and survivorship of the prosthesis.

Therefore, it would seem logical to develop an alternative bearing surface in total knee replacements to attempt to reduce wear by applying the newest generation of polyethylene in combination with the successful characteristics of a PS knee. On theoretical ground this knee prosthesis will potentially further improve survivorship and function of these implants. The Triathlon CS insert (Stryker, Warsaw, USA)

substitutes the posterior cruciate function (like normal PS knees) without the use of a post. This will remove the additional wear observed in PS knees without compromising function and stability. The insert is available in a conventional polyethylene (N2Vac) and the newest generation polyethylene (X3).

To test new bearing concepts on a large scale in a general population, using national registries as the primary benchmarking tool, is by definition not a good idea. Firstly, the main endpoint in registers is usually revision and all tribological failures, radiological or clinical, do not have to lead to revision. Secondly, due to the relatively low observed revision rate, the size of the population to be studied has to be large (several thousands) and to be followed over an extended period of time (5-10 years) in order to detect statistically significant differences (Robertsson, 2007). Therefore to study wear and fixation of new implants accurate outcome parameters have to be used.

Roentgen Stereophotogrammetric Analysis (RSA) is a very accurate measurement technique used to obtain micromotion of the implants relative to inserted tantalum markers in the surrounding bone. The accuracy of RSA mentioned in the literature ranges from 0.01 to 0.7 mm for displacement. It has been applied in many studies, mostly in Sweden (Kärrholm, 1989). In 2000, the Orthopaedic Department of the Leiden University Medical Center developed a Model-based RSA system (Model-based RSA, Medis specials BV, Leiden, The Netherlands). The accuracy of this software in clinical studies is about 0.25 mm for translations and 0.2° for rotations in the 95% confidence interval (Hurschler et al., 2006; Kaptein et al., 2003; Vrooman et al, 1998). Kärrholm et al. (1994) and Ryd et al. (1995) showed that with RSA a long-term prediction can be made of prosthetic loosening based on a two years follow-up.

The goal of this study is to compare conventional UHMWPE with X₃ highly cross-linked polyethylene in a CS fixed bearing total knee prosthesis (Triathlon Knee System: Stryker, Warsaw, USA) by means of RSA and clinical evaluation.

1.2. Description of the Devices

The Triathlon® Knee System (Stryker, Warsaw, USA) is designed to help provide patients more natural-like motion, a better anthropometric fit and the potential for greater implant longevity, e.g. in reduction of Polyethylene related wear. The design goal was to optimize rotation in deep flexion while providing stability. The unique design of the Triathlon Knee with its anatomic single-radius replicates proper tracking of the epicondyles, creating natural soft-tissue tension that promotes stability, allows for deep flexion and facilitates the tibial rotation necessary to support deep flexion activities. This will mimic natural knee motion, enhancing stability and mobility during daily activities. These design characteristics offer the potential for enhanced long-term component durability.

Triathlon Peri-Apatite coated Tibial component:

All tibial components are Peri-Apatite coated. The crystals deposited from the Peri-Apatite form a Hydroxy- Apatite coating with an overall average thickness of 20 µm which allows for bone in-growth.

Prostheses are available in eight different (1-8) so the best suited size is used for the patient based on the pre-operative evaluation and planning.

The participating surgeons will use Stryker instruments for prosthesis placement. The instruments will be used conform the instructions of the manufacturer.

(Cat. # 5526-B-X00 Triathlon Primary PA coated)

Triathlon Peri-Apatite coated Femoral component:

All femoral components are Peri-Apatite coated. The crystals deposited from the Peri-Apatite form a Hydroxy- Apatite coating with an overall average thickness of 20 µm which allows for bone in-growth.

Prostheses are available in eight different (1-8) so the best suited size is used for the patient based on the pre-operative evaluation and planning.

The participating surgeons will use Stryker instruments for prosthesis placement. The instruments will be used conform the instructions of the manufacturer.

(Cat. # 5517-F-XXX Triathlon CR PA coated)

Polyethylene insert N2Vac:

Ultra high molecular weight polyethylene (UHMWPE) is a linear polymer with a molecular weight of 4 – 6 Daltons. In solid form the crystallinity is about 50%. The numerous tie molecules connecting the crystalline regions give this polymer high impact and wear resistance. For over 40 years UHMWPE has been used as a bearing surface for total hip or knee joint replacement.

Packaging and sterilisation techniques are important factors affecting for the longevity of this material. The N₂Vac packaging process consists of two steps: Nitrogen packaging and Gamma irradiation to limit the risk of oxidation during irradiation.

(Cat. #: 5531-P-XXX Triathlon CS N₂Vac Insert)

Polyethylene insert X3™:

X3 polyethylene offers advanced mechanical strength, improved wear reduction and resistance to oxidation by placing the material through a sequentially irradiation and annealing progressive crosslinking process. This patented process preserves the polyethylene's microstructure for optimal strength and fatigue benefits. It makes X3™ suitable for higher stress applications such as knees, so these patients may benefit from the potentially longer wearing properties of a highly crosslinked material.

(Cat. # 5531-G-XXX Triathlon CS X3 Insert)

1.3. Beads

To evaluate the motion of the polyethylene bearing and micromotion of the prosthesis, at least three well-scattered tantalum balls (∅ 1.0 mm) have to be inserted into the tibia and femoral bone. To this end a special designed Ta-marker insertion device will be used according to instructions of the manufacturer (Halifax Biomedical, NS, Canada). The beads are not part of the Knee system itself. The bead inserter

device will be loaned to the hospital by Stryker for the duration of the clinical study (covered in study contract).

2. Objectives of the Clinical Investigation

- The primary objective is the assessment of the in vivo wear of the two randomized polyethylene inlay types N2Vac and X3 by means of Roentgen Stereophotogrammetry. It is expected that the X3 group will show significantly less wear after 5 years compared to the conventional N2Vac polyethylene group.
- The secondary objective is the assessment of prosthetic migration results after two years of the Triathlon CS Peri-Apatite coated tibial and femoral components by means of Roentgen Stereophotogrammetry. It is expected that due to the superior wear qualities of X3 polyethylene this group will show significantly less migration of the prosthesis' components after two-years compared to the components in the N2Vac group.
- The third objective will be the prediction of the long-term survival of the Triathlon CS Peri-Apatite coated tibial and femoral components based on the two-year migration patterns combined with clinical factors and radiographic aspects. In order to identify other clinical parameters besides wear influencing the fixation of the prosthesis components, clinical scores and radiographic aspects will be correlated with the RSA outcome. Subsequently, a long-term prediction can be for the Triathlon CS Peri-Apatite coated tibial and femoral components.

3. Design of the Clinical Investigation

3.1. Study Design

Single-Center Randomized Controlled Trial (RCT) to compare conventional UHMWPE with X3 highly cross-linked polyethylene in a CS fixed bearing total knee prosthesis.

All Patient recruitment and RSA image acquisitions will take place in: 't Lange Land Ziekenhuis, Zoetermeer.

The Quality Control of the RSA images and RSA image analysis will be carried out by the CRO (ClinFact, Leiden, the Netherlands).

3.2. Number of Subjects

RSA is able to measure wear with high accuracy. Previous RSA wear studies show that the expected wear rate is 0.13 ± 0.08 mm a year (Short et al., 2005; Kellett et al., 2004). A clinical relevant difference to detect differences in wear would be a standard deviation of 0.1 mm a year.

Group sample sizes of 27 patients in each group would achieve 95% power to detect a difference of -0.1 mm wear between the null hypothesis that both group means are 0 and the alternative hypothesis that the mean of group 2 is 0.1 with estimated group standard deviations of 0.1 and with a significance level (alpha) of 0.05 using a two-sided two-sample t-test.

However, in order to also achieve the third objective of this protocol whereby clinical parameters will be correlated with RSA results, more patients are needed to obtain stronger correlations with the important

clinical outcome parameters. Taking the latter in account and to compensate for possible lost to follow up, 50 patients will be recruited per study group.

3.3. Randomisation

After signing Informed Consent, the patients will be randomised in one of the two groups, the day before surgery. Randomization envelopes will be provided by Stryker to the primary investigator. The patient will receive either the **N₂Vac polyethylene** inlay or the **X3 polyethylene** inlay for their CS total knee. .

The principal investigator and the participating surgeons may dissent from the randomisation scheme based on intra-operative findings. This patient will be excluded from the study.

4. Eligibility

General inclusion/exclusion criteria for patients undergoing primary total knee arthroplasty will be used as guidelines for this study. Subjects selected for this evaluation must meet the following criteria in order to be enrolled in to the study:

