5.3. Randomization, Blinding and Treatment Allocation

The patients will be randomized to receive N2Vac polyethylene inlay or the X3 polyethylene inlay (see section 3.3). The randomization will occur via a random number generator (manual or computer). The doctor or other health care professional does not choose the participants for each group. For patients satisfying inclusion criteria, randomisation will occur by retrieving the next randomly generated group assignment. The patient, physiotherapist (for the clinical evaluation) and data analyzers (RSA data, clinical data, radiographic data and statistics) will be blinded. The PI and other participating surgeons have no influence on the collection of the (clinical) data and the data analysis.

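### Sections 3.3 and 9.3 allow patients to be excluded after randomisation, possibly with the arm known; settle suitability before the envelope is opened and analyse every opened assignment

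*Combined protocol and SAP*

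**What the plan says.** Section 3.3 states that, after consent, "the patients will be randomised in one of the two groups, the day before surgery". It continues: "Randomization envelopes will be provided by Stryker to the primary investigator". Section 5.3 adds that, for patients meeting the inclusion criteria, "randomisation will occur by retrieving the next randomly generated group assignment". Neither section says who opens the envelope, at what moment, or when the operating surgeon is told.

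Section 3.3 then allows departures: "The principal investigator and the participating surgeons may dissent from the randomisation scheme based on intra-operative findings". The consequence is that "This patient will be excluded from the study".

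On blinding, section 5.3 says: "The patient, physiotherapist (for the clinical evaluation) and data analyzers (RSA data, clinical data, radiographic data and statistics) will be blinded". Surgeons are not in that list. The safeguard given for them is that "The PI and other participating surgeons have no influence on the collection of the (clinical) data and the data analysis". It does not mention the operation itself or the decision to dissent.

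Section 9.3 lists protocol deviations, among them failure to follow the surgical protocol and failure to implant the study device. It says that in such cases the patient would probably be excluded and a termination form completed. Section 9 names no analysis population.

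Only the insert differs between arms. Section 1.2 says "All tibial components are Peri-Apatite coated" and says the same of the femoral components. Section 2 nevertheless compares two-year component migration between arms as the secondary objective, alongside wear as the primary.

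**The concern.** Randomisation makes the arms comparable at the moment of assignment. Removing a patient afterwards is harmless if the reason has nothing to do with the arm or with the outcome. It is a risk when whoever decides may know the arm and is reacting to something that could bear on the outcome. Intra-operative findings could be of that kind: exclusion criterion 17 in section 4.2 already concerns bone stock too poor to support or fix the prosthesis.

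Blinded RSA reading cannot repair this. The RSA baseline is the discharge film at 4 to 7 days (section 6.3), so a patient removed in theatre never enters the comparison.

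At stake is the false-positive rate of the between-arm comparisons. A lesser point is that a surgeon who knows the arm while preparing bone and fixing components could, in principle, let it influence operative choices that affect migration.

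**Working it through.** **Inputs from the documents.** 50 patients per group, two-sided two-sample t-test, alpha 0.05 (section 3.2). The documents give no migration SD and no expected number of dissents or excluded deviations.

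**The plan's own figure.** Section 3.2 states 27 per group for 95% power with difference 0.1 mm and SD 0.1 mm, a standardised difference of 0.1/0.1 = 1. The noncentral t calculation gives n = 26.99, so 27, with power 95.0%. The figure reproduces, and this point does not alter it.

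**Assumptions for the bound.** Migration is standard normal (unit: one SD) with no true insert effect. There are 50 patients per arm, with k exclusions in one arm and none in the other. The excluded patients are the k judged worst, and that judgement correlates r with later migration. The values of k and r show a range and are not estimates.

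**Shift in the depleted arm's mean.** Shift = −r × S(k)/(50 − k), where S(k) is the expected sum of the k largest of 50 standard normal values, found by numerical integration. For r = 1:
- k = 1: 2.249/49 = 0.046 SD
- k = 2: 4.104/48 = 0.086 SD
- k = 3: 5.733/47 = 0.122 SD
- k = 5: 8.527/45 = 0.190 SD

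At r = 0.5 and r = 0.3 these are multiplied by 0.5 and 0.3. For k = 5 that gives 0.095 and 0.057 SD.

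**False-positive rate of the two-sided 5% test, by simulation** (2,000,000 trials per row for perfect selection, 400,000 for partial correlation):

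| k excluded, one arm only | r = 0 | r = 0.3 | r = 0.5 | r = 1 (perfect) |
|---|---|---|---|---|
| 1 | 5.0% | 5.1% | 5.3% | 6.0% |
| 2 | 5.0% | 5.2% | 5.7% | 8.0% |
| 3 | 5.0% | 5.4% | 6.3% | 10.5% |
| 5 | 5.0% | 6.0% | 7.7% | 17.8% |

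Repeat runs differ by up to about 0.2 of a percentage point; the k = 5 entries came out at 5.9% to 6.0% for r = 0.3 and 7.6% to 7.8% for r = 0.5. As a cross-check, with 50 per arm a plain shift of 0.1 SD is declared significant 7.9% of the time and one of 0.2 SD 16.8%, in line with the table.

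**Exclusion before allocation.** Removing the 2k highest of 100 patients and then allocating the rest evenly leaves the rate at 5.0% for k = 1 and for k = 5 (500,000 trials). Before allocation, selection cannot depend on the arm, however strongly it depends on prognosis.

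**What is not calculated.** Arm-aware operative choice has no figure, because the documents give nothing from which to derive one.

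**The case against.** The strongest reply is that no bias is shown. The surgeon might not know the arm. Dissent must rest on operative findings, and both inserts are Triathlon CS inserts, so nothing suggests that the same finding would be judged differently by material. That is fair, and it is why the partial-correlation columns matter more than the perfect-selection one. It does not remove the point: the text permits an exclusion made knowing the arm and gives no rule to prevent or detect it.

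Existing controls do bear on operative choice. An experienced surgeon uses a standard approach (5.4), one site-specific procedure applies (6.1.4), the operative record captures bone removed, soft tissue released and deviations (section 6), and operator effects are evaluated (9.1). These leave the operative-choice worry possible but minor. They do not help with exclusions, and section 9.3 is not simply a control, because it is itself a second route out of the study.

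Section 4.3.1 keeps data already collected when a subject withdraws. A patient excluded in theatre has no post-operative RSA data to keep.

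Late opening may be harder than it sounds. The order of trialling, fixation and insert choice is in an instruction manual that is not among the documents, so feasibility is for the surgeons to confirm. Keeping opened assignments in the analysis does not depend on it.

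A reader might infer more: that surgeons are told the arm the day before, that they operate differently by arm, that any bias favours X3, or that 18% is the expected error rate. The documents support none of these. They are silent on disclosure, give no mechanism or direction, and the 18% needs five exclusions, all in one arm and all perfectly chosen.

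**Conclusion.** The point holds as an optional design improvement, led by the exclusion rule and supported by envelope timing. Sections 3.3 and 9.3 permit exclusions after randomisation that may be made knowing the arm. The probable effect is small. Under one-sided exclusion of 1 to 5 patients, the 5% test runs at 5.1% to about 6% for a correlation of 0.3, at 5.3% to just under 8% for 0.5, and at 6% to 18% only in the extreme case. If the exclusions are unrelated to outcome, it stays at 5%.

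This rests on normally distributed migration, 50 per arm before exclusions, and assumed counts and correlations. The table is framed for migration. The same exclusions also reach the wear comparison, but no fault in the wear measurement is claimed. Less arm-aware operative choice is a secondary benefit for migration that cannot be quantified.

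**What to change.** 1. **Section 3.3, with 5.3 aligned.** Decide intra-operative suitability first and log it with the reason. Then theatre staff open the next sealed, sequentially numbered envelope, at the latest moment the surgeons confirm is feasible, ideally once the tibial and femoral components are in place. Record the time of opening. Patients found unsuitable before opening are not randomised. Consent and pre-operative eligibility stay before surgery.

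2. **Exclusion rule in 3.3 and likely exclusion in 9.3.** Replace both with: any patient whose envelope has been opened is followed and analysed in the assigned arm wherever data exist, and every departure is recorded with its reason and the assigned arm. A patient without valid consent is a separate matter and needs its own sentence.

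**Cost.** Both insert materials must be on hand in the plausible sizes for each case. The operative record gains one time field. A few more patients may need to consent, since those found unsuitable in theatre no longer use an assignment. There are no extra visits and no change to the sample-size calculation. Surgeons must confirm feasibility first.

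**Limits.** If opening has to come before fixation, arm-aware choices are reduced but not removed. Post-operative care and weight bearing, left to the physician in 6.1.4, are unaffected. Part 2 is worth making even if late opening proves impractical.

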9.1. Statistical Methods

Continuous outcome variables and their differences will be analyzed with parametrical statistical techniques, such as t-tests, unless the normality assumption does not seem reasonable for the data, in which case non-parametric techniques will be considered e.g. Wilcoxon/Mann-Whitney tests.

Categorical outcome variables will be analyzed with chi-square tests and/or Fisher's exact tests (depending on the expected values in the categories). For the relevant parameters (subsidence, survival, pain and function) also the 95 percent confidence intervals will be calculated.

The effect of parameters such as age, sex and operators will be evaluated using multiple variate analysis. All data will be analyzed by blinded researchers.

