9.3. Protocol Deviations

Any deviation from this protocol will be recorded with an explanation for the deviation and reported to Stryker who is responsible for analysing them and assessing their significance. Protocol deviations will be reported to the METC according to the local METCs reporting procedures.

Protocol Deviations for this study include the following:

- Informed consent process is not carried out according to ISO 14155 Part 1.
- Subject enrolled does not meet the inclusion/exclusion criteria.
- Subject is not implanted with study device.
- Subject not seen in the specified follow-up window.
- Surgical protocol not followed.

If the site anticipates a possible protocol deviation, the investigator or study coordinator should contact Stryker for guidance. For the examples cited above, it is likely that the patient would be excluded, and a Study Termination form completed.

10. Quality Management

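### Sections 3.3 and 9.3 allow patients to be removed after randomisation, and section 9 defines no as-randomised set and requires no by-arm account of removals for the 5-year wear comparison

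*Combined protocol and SAP*

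**What the plan says.** **Timing and allocation (section 3.3).** After consent, "the patients will be randomised in one of the two groups, the day before surgery". On the envelopes: "Randomization envelopes will be provided by Stryker to the primary investigator". The principal investigator and participating surgeons "may dissent from the randomisation scheme based on intra-operative findings. This patient will be excluded from the study". The findings that would justify dissent are not listed.

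**Blinding (sections 5.3 and 9.1).** "The patient, physiotherapist (for the clinical evaluation) and data analyzers (RSA data, clinical data, radiographic data and statistics) will be blinded". Surgeons are not on that list, but section 5.3 adds: "The PI and other participating surgeons have no influence on the collection of the (clinical) data and the data analysis". Section 9.1 states: "All data will be analyzed by blinded researchers".

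**Deviations (section 9.3).** The list includes not receiving the study device, departure from the surgical protocol, and "Subject not seen in the specified follow-up window". For these, "it is likely that the patient would be excluded, and a Study Termination form completed". Deviations are recorded with an explanation, and the sponsor assesses their significance.

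**Withdrawal (section 4.3.1).** When a subject withdraws, data already collected enter the final analyses. After discontinuation, the subject is seen as clinically appropriate. Withdrawn subjects are not replaced.

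**Analysis (sections 9.1 to 9.3).** These sections name tests, rule out imputation and describe deviations. Neither they nor any other section defines an as-randomised, per-protocol or other analysis population.

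**The concern.** Randomisation protects the comparison of the two polyethylenes only if patients stay in the group to which they were allocated. Here one rule removes patients after allocation, and the person who triggers it is not listed as blinded. A second rule makes removal likely for events that can arise at any time up to 5 years, including a late visit at which the wear image was in fact obtained.

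Because no analysis set is defined, two teams could follow the plan and arrive at different 5-year sets from the same 100 patients. Because removals need not be shown by arm, an imbalance could go unseen. At stake is whether the primary result, wear after 5 years (section 2), is a randomised comparison or a comparison of patients selected afterwards.

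**Working it through.** **1. Reproduce the plan's sample size.** Section 3.2 gives difference 0.1, SD 0.1, two-sided alpha 0.05, two-sample t-test, 95% power and 27 per group. The exact noncentral t gives n = 26.99, so 27, with power 95.0%. The figure reproduces.

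**2. Is power at risk?** Section 3.2 recruits 50 per group. Power is 99.9% at 50 v 50 and 99.8% at 45 v 50. The share of each group that can be lost before power falls below 95% is 1 − 27/50 = 46%. Power is not the problem.

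**3. What happens to each type of removed patient?**
- *Dissent in theatre.* The RSA baseline is the discharge image (section 6.3). A patient excluded at surgery has no baseline unless follow-up continues, and section 3.3 provides for none. Retaining data already collected cannot supply a wear value.
- *Late 5-year visit.* The image exists. Section 4.3.1 speaks of a subject who withdraws. Whether that covers a subject excluded under section 9.3 is not stated.
- *Deviation before 5 years.* The documents neither continue nor forbid scheduled RSA after termination.

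**4. How large could the bias be?** The documents give no removal rate and no link between removal and wear, so these inputs are assumptions:
- q: share removed in an arm, 0 to 10%.
- rho: correlation between the reason for removal and wear, 0.3 to 0.5.
- Removal takes exactly the extreme tail of the reason variable.

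Shift in an arm's mean = rho × 0.1 × phi(z) / (1 − q), where z cuts off the share q. The bias is the difference in shift between arms.
- q = 10%: phi(1.2816) = 0.1755, and 0.1755/0.90 = 0.195. The shift is 0.3 × 0.1 × 0.195 = 0.0058 to 0.5 × 0.1 × 0.195 = 0.0097.
- q = 5%: phi(1.6449) = 0.1031, and 0.1031/0.95 = 0.1086. The shift is 0.0033 to 0.0054.

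The false-positive rate comes from the noncentral t with no true difference and n = 50(1 − q) per arm. For 10% v 0%, SE = 0.1 × √(1/45 + 1/50) = 0.0205.

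| Removed, arm A v arm B | Bias (rho 0.3 to 0.5) | False-positive rate |
|---|---|---|
| 10% v 10% | 0 | 5.0% |
| 10% v 5% | 0.0026 to 0.0043 | 5.2 to 5.5% |
| 5% v 0% | 0.0033 to 0.0054 | 5.3 to 5.8% |
| 10% v 0% (5 of 50 in one arm only) | 0.0058 to 0.0097 | 5.9 to 7.6% |

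A simulation of 200,000 trials agrees: 5.9% and 7.5% for 10% v 0%, and 5.2% and 5.6% for 10% v 5%. The bias carries the unit of section 3.2, which uses both mm and mm a year.

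A second model removes patients from one arm only whose wear is 0.5 to 1.0 SD higher. At 10% removal the bias is 0.10 × 0.5 × 0.1 = 0.005 to 0.10 × 1.0 × 0.1 = 0.010, with a false-positive rate of 5.7 to 7.7%.

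**5. What does analysis as randomised cost?** If 10% of one arm receives the other insert, the expected difference is 0.1 × (1 − 0.10) = 0.09. Power at 50 per group is 99.4% with SD 0.1. With the mixture variance 0.01 + 0.1 × 0.9 × 0.01 = 0.0109 in that arm, it is 99.2%.

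**The case against.** **No mechanism for differential removal is shown.** Both inserts are Triathlon CS and are described as differing in polyethylene (sections 1.1 and 1.2). Nothing in the documents suggests an intra-operative finding that favours one over the other. Every non-zero figure above needs unequal removal, a correlation with wear and strict tail removal. This stands, and it limits the size of the point.

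**Safeguards exist.** Analysts are blinded, surgeons have no influence on data collection or analysis, missed appointments trigger contact attempts, and removals and reasons are recorded. These are real. None of them restores a patient who has been removed, and none requires a by-arm report.

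**Section 4.3.1 may already keep the data.** Its list of reasons for withdrawal includes investigator decisions and device events, so withdrawal can reasonably be read to cover excluded subjects. On that reading a late 5-year image is kept. The wording is ambiguous, and a clarifying sentence would settle it.

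**A full as-randomised wear set is not attainable.** A patient who received neither insert has no wear that can be read as N2Vac or X3. Any primary wear set therefore depends on the insert received and an available image, and must be labelled as modified. For a question about two materials, analysis by insert received is also defensible, and it belongs among the sensitivity analyses.

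**Stronger readings to avoid.** A reader might infer that surgeons remove patients knowing the arm. The blinded list and the envelope route make such knowledge probable, but no sentence says so. A reader might also infer that excluded patients' data are discarded or that their RSA stops. The documents say neither.

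**Conclusion.** The point holds as a gap in the plan that should be fixed. The stated rules can remove evaluable patients after randomisation, no as-randomised set is defined, and removals need not be shown by arm. That much rests on the text alone.

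It would go too far to conclude that the wear comparison is biased. The documents give no rate of dissent or exclusion and no reason for dissent to differ by arm. The bias may be zero, and with equal removal under the model above it is. The illustrative range is 0 to 0.010, at most about 10% of the 0.1 target, with a false-positive rate of 5.0 to 7.6%. It rests on assumed removal of up to 10% in one arm and assumed correlations of 0.3 to 0.5. Nor would it be right to call the trial underpowered, since power stays at 99.8% with 45 v 50 patients. The case for change is that protection is cheap and that, as written, the plan could not show whether removals were balanced.

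**What to change.** 1. **Section 3.3.** Replace the exclusion sentence. A patient who received either study insert stays in scheduled follow-up and is analysed in the randomised group. A patient who received no study insert is counted by arm with the reason and kept in the clinical and safety summaries, but is not in the wear analysis. The surgeon's freedom to choose an implant is unchanged.
2. **Section 9.3.** Remove exclusion and termination as the consequence of post-randomisation deviations such as an out-of-window visit. Include out-of-window 5-year images in the primary analysis. Because the planned two-sample t-test takes no account of visit date, add wear divided by actual follow-up time as a sensitivity analysis.
3. **Section 9.** Define the primary wear set as all randomised patients with a study insert and a 5-year RSA measurement, analysed as randomised, and state that this is a modified as-randomised set. Give analyses by insert received and per protocol (defined blind to allocation) as sensitivity analyses. Tabulate all removals by arm and reason.
4. **Section 4.3.1.** State that data retention covers discontinued and excluded patients as well as those who withdraw.

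**Cost.** Protocol wording, and a table built from forms already completed (Study Termination forms and deviation records). The planned RSA visits and image readings must also be completed for the few patients who would otherwise have been removed. Crossovers dilute the difference slightly: power is 99.2 to 99.4% if 10% of one arm crosses over, at 50 per group.
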